4.2 Rationale for Dose and Regimen

LACTIN-V is available in a dose level of 5×10^9 CFU/applicator for this Phase 3 study in the rUTI population, which is the same dose studied in a Phase 1 Study and a Phase 2a BV study (Protocols LV-005 and LV-006, respectively). No serious adverse events have been reported.

Preliminary data from Protocol LV-001 have shown that subjects receiving LACTIN-V at the 5×10^8 CFU/capsule dose level had a 40% colonization rate (6/15 subjects) with the *L. crispatus* strain CTV-05, as compared to a 20% colonization rate (3/15 subjects) in the 5×10^6 CFU/capsule treatment group (Osel Inc., personal communication). At a dose of 2×10^9 CFU/applicator (Protocol LV-006), 61% of women randomized to the LACTIN-V group were colonized with *L. crispatus* CTV-05 at Day 10 or Day 28. Among LACTIN-V users with complete adherence to the study regimen, 78% were colonized at Day 10 or Day 28.

The dosing regimen selected for this study was based on the dosing regimen in the Phase 1 and 2a studies with LACTIN-V, in which subjects inserted one capsule daily for five consecutive days, followed by one applicator weekly for 2 weeks. In this Phase 3 study, as in Protocol UW/LB-001, subjects will receive one intravaginal applicator daily for five consecutive days (Days 1–5), followed by one applicator weekly for 10 weeks (starting on Day 8) for a total of 15 applicators over 11 weeks. Weekly dosing has been added for 10 weeks following the initial five-day course so that *L. crispatus* strain CTV-05 colonization can be maintained throughout the study period.

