4.4.2 Safety

Safety will be evaluated using the following safety measures:

1. Subjects will be queried about adverse events at all visits.
2. Subjects will be given a Study Diary to record symptoms.
3. Genital examinations at all visits. Complete pelvic exams at visit one and six or if clinically indicated.

4.4.3 *Lactobacillus* Colonization

Vaginal colonization with lactobacilli will be assessed by vaginal culture. This culture information will be both specific to *L. crispatus* CTV-05 and non-specific (total vaginal lactobacilli, including endogenous and exogenous lactobacilli).

Total *Lactobacillus* colonization and H₂O₂ production will be assessed using culture. Colonization specifically with *L. crispatus* CTV-05 will be assessed using a DNA fingerprinting technique known as rep-PCR (11), a repetitive element sequence-based PCR, which will be used to identify the specific strain of *L. crispatus* (CTV-05) by

amplifying its unique pattern of DNA fragments. This technique, which makes use of repetitive sequences dispersed throughout a bacterial genome for the direct amplification of genomic DNA, generates bacterial species- or strain-specific fingerprint patterns. Rep-PCR can be used to distinguish probiotic *L. crispatus* strain CTV-05 from other *L. crispatus* species. The *Lactobacillus* cultures and CTV-05 rep-PCR will be performed in the lab of [name]. at the University of Washington. The rep-PCR data collected will be used to assess the correlation between colonization and clinical endpoints.

Vaginal fluid specimens will be stored from each visit for analysis of shifts in the composition of vaginal microbiota by qualitative and/or quantitative DNA amplification methods. DNA amplification will be performed in the lab of [name] M.D. at the University of Washington.

4.4.4 *E. coli* Colonization

Vaginal colonization with *E. coli* will be assessed by vaginal culture at all visits. The *E. coli* cultures will be performed in the lab of [name]. at the University of Washington.

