5 STUDY DESIGN

5.1 Description of the Study

This is a Phase 3, randomized, double-blind, placebo-controlled study. Safety will be assessed using self-reported symptoms, pelvic examinations and vaginal cultures. The study will be conducted in 276 women with UTI symptoms and a history UTI in the past 12 months. The duration of the antibiotic course prior to study entry is anticipated to be 3–5 days, however the length of treatment will be decided by the treating provider.

At the Screening Visit (Visit 0), subjects will be evaluated for eligibility with a medical history, physical examination, genital examination and vaginal swabs for specimen collection.

If found eligible based on the results of the Screening Visit (v0), the subject will be prescribed antibiotics and scheduled to return for the randomization visit in 3-10 days after antibiotic completion. At Visit 1 subject will be randomized to receive either LACTIN-V at a dose of 5×10^9 CFU/applicator daily for five days followed by one applicator per week for 8 weeks or the placebo applicator on the same schedule. The LACTIN-V applicator will contain active *Lactobacillus* (strain CTV-05) in maltodextrin and a preservation matrix and the placebo capsule will contain maltodextrin and preservation matrix only. LACTIN-V is supplied as a powder formulation in a pre-filled, single-use applicator. The preservation matrix contains xylitol, trehalose, and sodium ascorbate. LACTIN-V placebo applicators contain 200 mg of the powder formulation without *L. crispatus* CTV-05.

Visit 0 (Screening Visit) will occur at the time of the UTI diagnosis. Visit 1 should occur within 3–10 days of completing antibiotic. Visit 2 will occur at Week 3, Visit 3 at Week 6, and visits will be monthly thereafter for 3 months.

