At Visit 1, each subject who continues to meet all inclusion and exclusion criteria will be randomized and will receive a box containing 15 applicators. Two extra applicators will be kept at the study site in case a lost or damaged applicator needs to be replaced. The first study applicator will be inserted under supervision in clinic at this visit. The remaining 14 applicators will be inserted daily at bedtime on Days 2–5, and then weekly. Women are to abstain from sexual intercourse and tampon use for 24 hours after each applicator is used. If the subject's partner uses condoms, they will be instructed to use non-spermicidal condoms to avoid killing the *L. crispatus*. The use of other intravaginal products including douching is prohibited throughout the four-month study period. Subjects must agree not to self-medicate with antibiotics or antifungals during the four-month study period. However, subjects may be treated for any on-study vaginal or other infection if a health care provider deems such treatment necessary. Subjects who receive antibiotic or antifungal treatment after commencing the study should continue to insert the study applicator according to their allocated schedule.

Subjects will be provided with a Study Diary to use to record applicator use information during the study. The Study Diary will also be used by subjects to record any symptoms. Subjects will be instructed on how to use these memory aids to remind them to insert the applicator on the designated day and to record the date and time when each applicator was inserted.

Self-reported symptoms will be evaluated at all study visits. Subjects will be queried about the following symptoms:

Nausea or vomiting
Abdominal Discomfort
Diarrhea
Constipation
Rash
Abnormal Vaginal Discharge/Bleeding
Abnormal Vaginal Odor
Genital itching or burning
External genital irritation/swelling
Painful Urination
Urinary Frequency
Urinary Urgency
Blood in urine

Headache
Other: _____

Other: _____

Subjects will be instructed to call the study clinic if they have any unexpected symptoms at any time during the study.

Pelvic examinations will be performed at all visits to evaluate the external genitalia; cervix and vaginal mucosa for signs of irritation at Visits 1 and 6 and if clinically indicated.

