6.4.2 Investigational Product Instructions

At Visit 1 (Randomization Visit), each study subject will be counseled on how to use the applicators. Written instructions for administration, storage and handling will be provided to each study subject (Appendix B), along with a Study Diary to record applicator use times and symptoms throughout the study. Each subject will be instructed to use the applicator on scheduled days, and weekly insertion dates will be marked on the Study Diary, which the subject will take home.

Instructions will be given regarding what to do in the event that the subject forgets to use an applicator on the prescribed day (see Section 6.6).

Subjects will be instructed to defer insertion of applicators on days of heavy menstrual flow.

Information will be reviewed with the study subject at each of the follow-up visits, and study personnel will address any questions or concerns that may arise.

Subjects will be asked to return both used and unused applicators.

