10.2 Secondary Endpoints

The secondary endpoints of this study are parameters of vaginal environment and colonization and adverse events due to the study product.

1. Vaginal colonization with total lactobacilli (as assessed by vaginal culture) and *Lactobacillus crispatus* strain CTV-05 (as assessed by rep-PCR) at Visits 1 through 6 in the LACTIN-V group (Group A) as compared to the placebo group (Group B).
2. Vaginal colonization with *E. coli*, in the LACTIN-V group (Group A) as compared to the placebo group (Group B), as assessed by the presence of *E. coli* on vaginal culture at Visits 1 through 6.
3. Shifts in the vaginal microbiota of individual subjects, as assessed by Nugent score of vaginal gram stains at Visits 1 through 6, in the LACTIN-V group (Group A) as compared to the placebo group (Group B).
4. Shifts in the composition of vaginal microbiota, as assessed by qualitative and/or quantitative DNA amplification of stored vaginal specimens from all visits.
5. Presence and/or quantitation of H₂O₂, lactic acid, and cytokine profiles at Visits 1 through 6, in the LACTIN-V group (Group A) as compared to the placebo group (Group B).
6. Safety and tolerability will be evaluated by the number (%) of subjects with any treatment emergent adverse event, reported symptoms and/or abnormal pelvic examination results over the four-month study period.

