Appendix B

Study Diary Instructions

The "Diary" on the other side will help you to record when you insert your study applicators. Please mark the daily boxes to record any activity or symptoms.

When to Insert the Study Applicator

You will use the first applicator in the clinic on Day 1. All other applicators will be used at bedtime.

Starting tomorrow evening, you will insert an applicator at bedtime. Continue using one applicator a day at bedtime. For the first week, you will be inserting an applicator daily for 5 days. In the following weeks, it will be done once a week. The study staff will mark your diary for the recommended SCHEDULED DATE.

If you forget to insert the applicator please insert it as soon as you remember.

Recording When You Insert the Study Applicator: Use the Diary on the Other Side

Write the date and time in the Diary box for each applicator that you insert (Dose 1, Dose 2, etc.). If you insert your applicator after midnight, record the actual date and time of insertion.

Recording Activity

Check the box for each day on which an activity occurred.

Recording Symptoms

Write **1=Mild, 2=Moderate or 3=Severe** in the box for each symptom you have during the first 7 days of the study.

To Insert A An Applicator

Wash your hands thoroughly with warm water and soap.

Open **one** applicator package. Do not use anything sharp, like scissors, which could damage the applicator.

Holding the applicator between your thumb and fingers, insert into the opening of the vagina (like a tampon), and push plunger to dispense the contents.

Storage and General Instructions

Store the applicators in their box at room temperature until use.

Please avoid having sexual intercourse for 24 hours after use or use the condoms provided by the study.

Do not use another vaginal product, such as contraceptive creams, gels, foams, sponges, lubricants, douches, etc. during this study unless your doctor prescribes it.

Do not use tampons for 24 hours after applicator use.

Do not insert the applicator if you are having heavy bleeding from your period.

If you lose or damage an applicator, use another instead. If you somehow lose or damage more than 2 applicators or the whole box, please call the study clinic immediately for further instructions.

Place used applicators back in their original pouches and return at clinic visits, and return any unused applicators at the end of the study.

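### Appendix B limits diary symptom scoring to the first 7 days, in conflict with section 6.4.2; if women follow it, no weekly dose has diary symptom scores

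*Combined protocol and SAP*

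**What the plan says.** Appendix B is the sheet that women take home. Its paragraph on recording symptoms asks for a severity code from 1 (mild) to 3 (severe) "in the box for each symptom you have during the first 7 days of the study". No other instruction in the sheet says how to score a symptom. The sheet opens, however, with a general request that has no time limit: "Please mark the daily boxes to record any activity or symptoms".

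The protocol body describes a longer record:

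- Section 6.4.2 says that each woman receives written instructions "along with a Study Diary to record applicator use times and symptoms throughout the study".
- Section 4.4.2 lists the diary as one of the safety measures: "Subjects will be given a Study Diary to record symptoms".
- Section 5.1 says "The Study Diary will also be used by subjects to record any symptoms", with no end date.
- The flow chart has the diary dispensed at Visits 1 to 6 and reviewed at Visits 2 to 6.

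The safety endpoint in section 10.2 counts subjects with treatment-emergent adverse events, "reported symptoms and/or abnormal pelvic examination results over the four-month study period".

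On timing of doses, section 4.2 has five daily applicators "followed by one applicator weekly for 10 weeks (starting on Day 8) for a total of 15 applicators over 11 weeks". Section 5.1 instead has dosing "daily for five days followed by one applicator per week for 8 weeks" and gives no day for the first weekly dose.

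**The concern.** The woman works from Appendix B, not from section 6.4.2. If she takes the scoring line at its word, she stops scoring symptoms after Day 7, just before weekly dosing begins. The diary would then describe the run of daily doses and none of the weekly ones.

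The weekly phase is where this matters. In section 2.2.2.2, LV-003 (five daily and then ten weekly capsules) reported nausea, diarrhea, dysuria, vaginal discharge and vaginal odour more often on LACTIN-V, by at least 5%. The applicator studies described there were shorter: five daily doses in LV-005, and five daily doses plus weekly use over 2 weeks in LV-006. Longer weekly use of the applicator is thus where the protocol reports least experience with this delivery form.

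At stake is a same-day record of onset and severity that can be tied to a particular applicator. Daily scores that were never written down cannot be recovered later.

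**Working it through.** **Passages side by side**

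| Place | Period for diary symptoms |
|---|---|
| Appendix B, symptom paragraph | Days 1 to 7 |
| Appendix B, opening line | no limit stated |
| Section 4.4.2 | no limit stated |
| Section 5.1 | no limit stated |
| Section 6.4.2 | whole study |
| Flow chart | dispensed Visits 1 to 6, reviewed Visits 2 to 6 |

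The first row cannot be reconciled with the fifth, and it does not fit the others.

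**Step 1. Reproduce the schedule in section 4.2.** Daily doses fall on Days 1 to 5. Weekly dose i falls on Day 8 + 7(i − 1). The total is 5 + 10 = 15 applicators. The last is on Day 8 + 7 × 9 = 71, and 71/7 = 10.1, so it lies in week 11. This agrees with the stated 15 applicators over 11 weeks.

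**Step 2. Count weekly doses inside Days 1 to 7.**

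- Section 4.2 schedule: the earliest weekly dose is on Day 8, so 0 of 10.
- Section 5.1 schedule: 5 + 8 = 13 applicators, which matches the total in section 6.7. With a Day 8 start, the last dose is on Day 8 + 7 × 7 = 57, and 0 of 8 fall inside. If the first weekly dose came a week after the last daily one, on Day 12, the count is still 0 of 8.
- Appendix B itself places the weekly doses in the weeks after the first, so the result does not depend on which schedule applies.

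**Step 3. Share of applicators without diary scores around them.** 10/15 = 67%, or 8/13 = 62%.

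**Step 4. Share of follow-up inside the window.** Over the 16 weeks of section 10.1, 7/112 = 6.3%. If the last visit is at Week 18 (section 10.3 and the flow chart), 7/126 = 5.6%.

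**Step 5. Recall interval if the diary stops.** Section 10.3 has visits at Weeks 3, 6, 10, 14 and 18, so gaps of 3, 3, 4, 4 and 4 weeks. Section 4.3 has Weeks 2, 4, 8, 12 and 16, so gaps of 2, 2, 4, 4 and 4 weeks. The longest gap is 4 weeks either way. One visit question can therefore span about four weekly doses: on the ten-week schedule, those on Days 43, 50, 57 and 64 lie between Week 6 (Day 42) and Week 10 (Day 70).

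**Step 6. Effect of aligning Appendix B with section 6.4.2.** All weekly doses come inside the scoring period: 10 of 10, or 8 of 8.

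The documents give no figure for how many symptoms are missed by recall compared with a daily diary, so the loss itself cannot be calculated.

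**The case against.** The strongest reply is that the safety endpoint does not depend on the diary. Section 5.1 has a list of 14 named symptoms asked about at all visits. Section 6.9.3 asks at Visits 2 to 6 about symptoms during or after applicator use. Section 10.3 assesses safety at each visit from self-reported events, symptoms and examination findings, and section 7.1.1 tells women to call or come in with unexpected symptoms. Neither Table 1 nor section 10.10.5 names a diary-based analysis. This stands: four-month coverage exists without the diary.

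It can also be said that recall loss would affect both blinded arms, so no bias between arms has been shown. That stands too. It does not restore the severity, the dates or the link to a given dose, and section 4.4.2 lists the diary as a safety measure in addition to the visit questions.

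Thirdly, the diary form is Appendix C, which is attached separately and not in the available text. Its symptom boxes may run past Day 7, and the opening line of Appendix B would support that. This is why the point is conditional. It does not remove the conflict, because the specific scoring line still says 7 days.

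Finally, a 7-day window might be deliberate, as a record of early reactions to the daily doses. If so, section 6.4.2 is wrong, and one of the two passages must still change.

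**Conclusion.** The 7-day line in Appendix B contradicts section 6.4.2 and does not fit sections 4.4.2 and 5.1, the flow chart or the sheet's own opening line. If women follow it, none of the 8 or 10 weekly doses (62% or 67% of applicators) has diary symptom scores, and symptoms around those doses rest on recall over as much as about 4 weeks. The count of zero holds under either dosing schedule. It assumes that women follow the specific scoring line over the general opening line, and that the Appendix C form does not prompt them otherwise.

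A reader might infer three stronger things, none of which the documents support:

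- **That the plan has no diary symptom data for the weekly doses.** Section 6.4.2 calls for them; the fault is that the participant sheet contradicts it.
- **That the four-month safety endpoint is left without data.** Symptom, adverse-event and examination data from visits cover it. Under-recording of mild symptoms is plausible but not quantified.
- **That dating of UTI suffers.** Sections 10.1, 10.3 and 10.9.3 measure time to recurrence to the date of diagnosis, so diary onset dates enter no stated UTI analysis.

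The correction should be made. Safety information is weakened, not lost, and the efficacy analysis is unaffected.

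**What to change.** Reword the scoring line in Appendix B so that a severity code is given for each symptom during the study, which brings it into line with section 6.4.2. Check that the Appendix C form has symptom boxes for the same period and add them if it does not. If daily boxes throughout are thought too heavy, cover at least the days around each weekly applicator and word section 6.4.2 to match.

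If the 7-day window was intended, correct section 6.4.2 instead and state that symptoms after Day 7 rest on visit questions. That resolves the contradiction but gives up the prospective record.

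The cost is one line of instruction, perhaps a diary page, and slightly more work for participants. Randomization, sample size and dosing are untouched. The conflict between 8 and 10 weekly doses, and between 13 and 15 applicators, needs separate reconciliation; the diary form should be laid out for whichever schedule is confirmed.

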Appendix C

Study Diary: see attached
